### 9.4 STATISTICAL ANALYSES

#### 9.4.1 GENERAL APPROACH

Descriptive statistics (e.g. means, standard deviations or medians and interquartile range for continuous data; frequencies and percentages for categorical data) will be calculated for the patients who meet the final inclusion/exclusion criteria.

For descriptive purposes, the overall crude estimates of the incidence of any SSO or any SII will be calculated. These incidences will also be expressed per 100 or 1,000 or 10,000 patients. The chi-square test or Fisher's exact test will be used to compare the crude incidence rates of any SSO or any SII between study groups (NPWT vs. SOC).

For continuous and ordinal variables, data will be expressed as a median with interquartile range. For dichotomous variables, percentages will be calculated. Comparisons will be performed with the Mann-Whitney test for continuous variables as appropriate. Comparisons of percentages will be performed with the Fisher Exact test as appropriate.

The incidence of SSI and SSO per 100 patients between groups will be compared. Risk ratios (RR), 95% CIs and p values assuming a 5% significance level will be presented.

For the primary outcome, the number needed to treat and absolute risk reduction will be calculated from the RR. While we do not anticipate differences between groups in terms of known or unknown prognostic factors because of randomization, adjusted analyses using multivariate logistic regression models will be used if any difference in prognostic variables is detected.

Covariates will be prespecified:

- Medical comorbidities
  - Hypertension (pregestational and gestational)
  - Diabetes (pregestational and gestational)
  - HIV
- Smoking status
- Prior cesarean delivery
- Steroid exposure (betamethasone) within 2 weeks of surgery
- Need for preoperative hair removal (particularly shaving)

Checks of assumptions (e.g., normality) underlying statistical procedures will be performed and whether any indicated corrective procedures will be applied (e.g., transformation or nonparametric tests).

A mixed model approach (generalized linear mixed model [GLMM]) will be used to examine the incidence of SSOs and SIs (separately) between study groups, and other factors of interest such as medical comorbidities (Hypertension, Diabetes, HIV status), smoking status, prior cesarean delivery, steroid exposure within 2 weeks of surgery, and need for preoperative hair removal. Adjusted Incidence Rate Ratios [IRR] and their associated confidence intervals will be obtained from this approach.

If feasible, a sub-analysis will be performed according to the following BMI stratification of the study participants: 35 – <40 kg/m^2, 40 – <45 kg/m^2, 45 – <50 kg/m^2, ≥50 kg/m^2.

---

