### 9 STATISTICAL CONSIDERATIONS

#### 9.1 STATISTICAL HYPOTHESES

- Primary Efficacy Endpoint(s):

The Smith and Nephew PICO NPWT dressing is superior to the standard cesarean incision dressing in preventing surgical site occurrences.

Null: The Smith and Nephew PICO NPWT dressing is NOT superior to the standard cesarean incision dressing in preventing surgical site occurrences.

- Secondary Efficacy Endpoint(s):

The Smith and Nephew PICO NPWT dressing is superior to the standard cesarean incision dressing in preventing surgical site infections.

Null: The Smith and Nephew PICO NPWT dressing is NOT superior to the standard cesarean incision dressing in preventing surgical site infections.

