#### 9.2 SAMPLE SIZE DETERMINATION

- Outcome measure used for calculations (almost always the primary variable): incidence of surgical site occurrences.
- Type I error rate (alpha): 0.05 (5%)
- Power level: 80%

Based on results from several clinical studies and the American Congress of OBGYN Practice Bulletin on Obesity in Pregnancy, we estimate the proportion of subjects with surgical site occurrences among obese women who undergo elective cesarean surgery to be about 18%. We accept that an absolute difference between study groups of 10%, will be a clinically meaningful difference. Therefore, a chi-square test will yield 80% power to detect a clinically important difference of 10% between study groups (SOC proportion of 18% vs. PICO NPWT proportion of 8%, an odds ratio of 0.396) when the sample size

in each group is 180 *evaluable* subjects. Assuming an attrition rate of about 10%, we would need to recruit about 200 subjects per group (180/0.90=200 subjects).

Note: A study participant is considered 'evaluable' if she has completed all phases of the study including the last visit of the last scheduled procedure in the schedule of activities, i.e. the final study visit 4—day 42±10 days post-op.

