#### 9.4.3 ANALYSIS OF THE SECONDARY ENDPOINT(S)

Secondary endpoint: Incidence rate of surgical incision intervention (SII) post Cesarean delivery.

Interventions include:

- Antimicrobials for surgical site infection. This is a binary nominal categorical variable that will be measured as a repeated measure. Analysis of this secondary endpoint is dependent on findings of primary endpoints.
- Surgical drainage of the incision. This is a binary nominal categorical variable that will be measured as a repeated measure. Analysis of this secondary endpoint is dependent on findings of primary endpoints.
- Surgical incision packing. This is a binary nominal categorical variable that will be measured as a repeated measure. Analysis of this secondary endpoint is dependent on findings of primary endpoints.
- Adjunctive negative pressure therapy (i.e. need for wound vac therapy). This is a binary nominal categorical variable that will be measured as a repeated measure. Analysis of this secondary endpoint is dependent on findings of primary endpoints.
- Debridement. This is a binary nominal categorical variable that will be measured as a repeated measure. Analysis of this secondary endpoint is dependent on findings of primary endpoints.
  - Re-operation. This is a binary nominal categorical variable that will be measured as a repeated measure. Analysis of this secondary endpoint is dependent on findings of primary endpoints.

The results of statistical procedure(s) will be presented as odds ratios with 95% confidence intervals, and number-needed-to-treat.

Missing data will be handled (e.g., type of imputation technique, if any, and provide justification), and approach to handling outliers, nonadherence and lost to follow-up by reporting this data as missing (and the reason why) and including all available data in the analysis.

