#### 9.4.9 EXPLORATORY ANALYSES

Not applicable.

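### The secondary hypothesis is SSI in section 9.1 but SII elsewhere, and neither the SSI test nor the any-SII test is clearly conditional on a significant SSO result

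*Protocol*

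**What the plan says.** - **Alpha.** Section 9.2 sets a type I error rate of 0.05 for one outcome, the incidence of SSO: "a chi-square test will yield 80% power to detect a clinically important difference of 10% between study groups", with 180 evaluable subjects per group.
- **Hypotheses.** Section 9.1 states the primary hypothesis for SSO. As its secondary efficacy hypothesis, with its own null, it states: "The Smith and Nephew PICO NPWT dressing is superior to the standard cesarean incision dressing in preventing surgical site infections". SII does not appear in 9.1.
- **Endpoints.** The synopsis, the table in section 3 and section 9.4.3 name one secondary endpoint, the incidence of SII. SSI appears there only as one of the five components of SSO.
- **Tests.** Section 9.4.1 introduces crude estimates of any SSO and any SII as descriptive, then uses the chi-square or Fisher's exact test to "compare the crude incidence rates of any SSO or any SII between study groups (NPWT vs. SOC"). Further on, it says that SSI and SSO will be compared between groups, and continues: "Risk ratios (RR), 95% CIs and p values assuming a 5% significance level will be presented".
- **Conditions.** Section 9.4.3 attaches to each of the six SII items a remark that its analysis depends on what the primary endpoints show. It then says: "The results of statistical procedure(s) will be presented as odds ratios with 95% confidence intervals, and number-needed-to-treat". No such remark is attached to SSI, or to the any-SII comparison in 9.4.1.

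**The concern.** The sections disagree on which outcome is the secondary one. The only conditional wording in the plan sits on the outcome that has no formal hypothesis (SII), while the outcome that has one (SSI) carries no condition. If the SSO test fails and SSI gives p < 0.05, the plan as written supports a statement that PICO is superior on SSI. The same can be argued for any SII, because the test in 9.4.1 carries no condition and the remark in 9.4.3 does not say whether it requires a significant SSO result or merely that SSOs have occurred.

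Two outcomes then compete for the role of key secondary, each at the full 5%. If the choice is made after results are seen, it will look post hoc even if it was made in good faith.

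**Working it through.** **Step 1: the plan's own figure.** Inputs from section 9.2 are 18% vs 8%, alpha 0.05 and 80% power; 1:1 allocation is from section 6.3. Sidedness is not stated. Without continuity correction, with mean proportion 0.13:

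n = [1.96·√(2·0.13·0.87) + 0.8416·√(0.18·0.82 + 0.08·0.92)]² / 0.10² = (0.932 + 0.396)² / 0.01 ≈ 176.4, so 177 per group.

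This is close to the stated 180, at which power is 80.8%. A one-sided test would need 139 (159 with continuity correction). The plan is therefore taken as two-sided 5%, which is 2.5% in favour of PICO. Recruitment is 180/0.90 = 200, as stated.

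**Step 2: which secondary tests have no clear condition?**

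| Outcome | Formal hypothesis (9.1) | Named secondary endpoint (synopsis, 3, 9.4.3) | Test stated in 9.4.1 | Condition stated |
|---|---|---|---|---|
| SSI | yes | no | yes, p value at 5% | none |
| Any SII | no | yes | yes, chi-square or Fisher | none in 9.4.1; undefined remark on the items in 9.4.3 |
| Six SII items | no | as its constituents | no | undefined remark in 9.4.3 |
| Other four SSO components | no | no | no | not applicable |

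SSI is clearly unconditional and any SII arguably so. That makes a family of two tests.

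**Step 3: false-positive rate for two tests.** If independent:

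- either direction: 1 − 0.95² = 9.75%
- in favour of PICO: 1 − 0.975² = 4.9%

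The outcomes overlap, because antimicrobials for SSI count as an SII. The documents give no correlation, so a range is assumed. Simulated equicorrelated normal test statistics give:

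| Assumed correlation | Either direction | In favour of PICO |
|---|---|---|
| 0 (formula) | 9.75% | 4.9% |
| 0.3 | 9.5% | 4.8% |
| 0.5 | 9.0% | 4.5% |
| 0.7 | 8.4% | 4.2% |
| 0.8 | 7.9% | 3.9% |

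SSI alone carries 5%, or 2.5% in favour of PICO.

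**Step 4: binary data.** With 180 per arm and assumed rates of 9% for both SSI and SII, simulation over correlations 0 to 0.8 gives 9.2% to 10.2% when the chi-square test is used (Fisher where expected counts are below 5). With Fisher's test throughout it gives 6.1% to 6.5%. As a cross-check, exact enumeration gives Fisher's test a true two-sided error of 3.21% at a 10% event rate, and 1 − (1 − 0.0321)² = 6.3%.

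**Step 5: effect of a gate.** If a secondary claim requires a significant SSO result, then with no true difference on any outcome the chance of a false secondary claim cannot exceed that of a false SSO result: 5%, or 2.5% in favour of PICO. If SSO truly differs, the gate is usually open, and two unordered tests behind it could again approach the rates in step 3. The plan therefore needs one named secondary or a stated order, not only a common gate.

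**The case against.** The strongest counter-argument is that testing order and alpha allocation among secondaries are commonly left to a statistical analysis plan, which is not shown here. Section 9.2 gives alpha to a single primary outcome, section 9.4.3 does contain a dependence on the primary endpoint, and the any-SII comparison follows estimates introduced as descriptive. In the direction that matters, two tests give less than 5%.

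Much of this stands, and it limits the size of the point. It does not remove it. The disagreement between 9.1 and the endpoint sections is in the protocol's own text, and an analysis plan could settle it only by departing from one of them. The dependence remark, read as generously as possible, still does not reach SSI. The comparator for 4% to 5% in favour of PICO is 2.5%, not 5%.

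A reader might go further and infer that SSI, SII, all six SII items and all SSO components are each tested at 5% with no hierarchy. The documents do not support that:

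- The sentence on the 5% level follows one that names only SSI and SSO.
- Sections 9.4.2 and 9.4.3 promise odds ratios, confidence intervals and number needed to treat. They state no p value or significance level for individual items.
- The items are listed as what SSO and SII comprise.
- The remark in 9.4.3 is a hierarchy of a kind, though a vague one.

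Nor does section 9.4.9, headed "EXPLORATORY ANALYSES" and marked not applicable, make the components confirmatory. It says only that no separate exploratory analyses are planned.

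**Conclusion.** The point holds in a limited form. The protocol names two different secondary outcomes, gives the formal hypothesis to the one with no condition, and leaves the condition on the other undefined. A superiority claim on SSI, and arguably on any SII, would remain open after a failed SSO test.

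The chance of at least one false positive across the two tests is about 8% to 10% two-sided, about 6% if Fisher's test is used throughout, and about 4% to 5% in favour of PICO against a nominal 2.5%. These figures assume a two-sided 5% level, correlations from 0 to 0.8 and, for the Fisher figure, event rates of 9%. They count a false positive on either secondary whether or not SSO is significant.

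A reader might infer that a chance superiority finding is likely. That is not supported. Eight tests (SSI, any SII and the six SII items) would give 15.7% to 33.6% two-sided over the same correlations, but only if the items were tested for claims, which the protocol does not state. Even that is well short of likely.

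**What to change.** Make sections 9.1, 9.4.1 and 9.4.3 agree:

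1. Name one key secondary, any SII being the endpoint already declared in the synopsis and section 3. Alternatively, keep both and state an order of SII and SSI.
2. State that it is tested for a claim only if any SSO is significant at two-sided 0.05, with a second outcome in the order tested only if the first is significant. Replace the dependence remark in 9.4.3 with this rule.
3. Always report the key secondary with its estimate and 95% confidence interval, whatever the SSO result.
4. Label the SSO and SII components, and SSI if it is outside the sequence, as supportive: estimates and confidence intervals, no superiority claim.

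This costs wording only and leaves 180 evaluable and 200 recruited per group unchanged. The price is that an outcome outside the sequence, which may be SSI, can no longer support a confirmatory claim. The change should be made before any results by group are seen.

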#### 9.4.2 ANALYSIS OF THE PRIMARY EFFICACY ENDPOINT(S)

Primary endpoint: the incidence of postoperative surgical site occurrences (SSOs) post cesarean delivery. SSOs include:

- Unanticipated local inflammatory response – measured by redness, tenderness, warmth, or induration on exam. This is a binary nominal categorical variable that will be measured as a repeated measure.

- Prolonged drainage – measured as drainage from surgical skin site  $\geq 3$  days from time of surgery. This is a binary nominal categorical variable that will be measured as a repeated measure.
- Fluid collection – measured as need for skin opening to drain fluid collected (seroma) underneath the skin wound. This is a binary nominal categorical variable that will be measured as a repeated measure.
- Dehiscence – measured as opening of skin wound  $\geq 2$ mm. This is a binary nominal categorical variable that will be measured as a repeated measure.
- Surgical site infection (SSI) - measured by redness, tenderness, warmth, or induration on exam with subject fever or purulent drainage. This is a binary nominal categorical variable that will be measured as a repeated measure.

The results of statistical procedure(s) will be presented as odds ratios with 95% confidence intervals, and number-needed-to-treat.

Missing data will be handled (e.g., type of imputation technique, if any, and provide justification), and approach to handling outliers, nonadherence and lost to follow-up by reporting this data as missing (and the reason why) and including all available data in the analysis.

---

#### 9.4.3 ANALYSIS OF THE SECONDARY ENDPOINT(S)

Secondary endpoint: Incidence rate of surgical incision intervention (SII) post Cesarean delivery.

Interventions include:

- Antimicrobials for surgical site infection. This is a binary nominal categorical variable that will be measured as a repeated measure. Analysis of this secondary endpoint is dependent on findings of primary endpoints.
- Surgical drainage of the incision. This is a binary nominal categorical variable that will be measured as a repeated measure. Analysis of this secondary endpoint is dependent on findings of primary endpoints.
- Surgical incision packing. This is a binary nominal categorical variable that will be measured as a repeated measure. Analysis of this secondary endpoint is dependent on findings of primary endpoints.
- Adjunctive negative pressure therapy (i.e. need for wound vac therapy). This is a binary nominal categorical variable that will be measured as a repeated measure. Analysis of this secondary endpoint is dependent on findings of primary endpoints.
- Debridement. This is a binary nominal categorical variable that will be measured as a repeated measure. Analysis of this secondary endpoint is dependent on findings of primary endpoints.
  - Re-operation. This is a binary nominal categorical variable that will be measured as a repeated measure. Analysis of this secondary endpoint is dependent on findings of primary endpoints.

The results of statistical procedure(s) will be presented as odds ratios with 95% confidence intervals, and number-needed-to-treat.

Missing data will be handled (e.g., type of imputation technique, if any, and provide justification), and approach to handling outliers, nonadherence and lost to follow-up by reporting this data as missing (and the reason why) and including all available data in the analysis.

#### 9.4.4 SAFETY ANALYSES

Safety endpoints will be analyzed as summary statistics during treatment.

#### 9.4.5 BASELINE DESCRIPTIVE STATISTICS

The following demographic data will be collected for descriptive statistics and will be compared between groups using inferential statistics:

- Age
- Race
- Ethnicity
- Gravidity/Parity
- Prior Cesarean delivery
- Gestational age (weeks)
- BMI (kg/m^2)
- Indication for cesarean delivery
- Medical comorbidities
  - Hypertension (pregestational and gestational)
  - Diabetes (pregestational and gestational)
  - HIV
- Smoking status
- Steroid exposure (betamethasone) within 2 weeks of surgery
- Need for preoperative hair removal (particularly shaving)

#### 9.4.6 PLANNED INTERIM ANALYSES

There are no planned formal interim analyses.

#### 9.4.7 SUB-GROUP ANALYSES

Sub-group analysis based on demographic data such as age, sex, or race are not warranted. This study intervention is only meant for use in a population of reproductive-age women undergoing cesarean delivery for this purpose.

Sub-group analysis will be performed by BMI: 35 – 39.9 kg/m^2, 40 – 44.9 kg/m^2, 45 – 49.9 kg/m^2, 50 – 54.9 kg/m^2.

#### 9.4.8 TABULATION OF INDIVIDUAL PARTICIPANT DATA

Data will be collected at baseline, and participants followed up on the first and postoperative day, the PICO group will be telephoned on postpartum day 5 or 6, and then at two postpartum visits: the 7 – 14 day incision check and the 6-week postpartum visit.

#### 9.4.9 EXPLORATORY ANALYSES

Not applicable.

### 10 SUPPORTING DOCUMENTATION AND OPERATIONAL CONSIDERATIONS

#### 10.1 REGULATORY, ETHICAL, AND STUDY OVERSIGHT CONSIDERATIONS

##### 10.1.1 INFORMED CONSENT PROCESS

###### 10.1.1.1 CONSENT/ASSENT AND OTHER INFORMATIONAL DOCUMENTS PROVIDED TO PARTICIPANTS

Consent forms describing in detail the study intervention, study procedures, and risks are given to the participant and written documentation of informed consent is required prior to starting intervention/administering study intervention. The following consent materials are submitted with this protocol:

Informed consent document attached to this IRB submission.

Smith & Nephew PICO Patient Information:

<https://www.smith-nephew.com/global/assets/pdf/products/wound/31447%20uk%20pico%20patient%20info%20leaflet.pdf>

###### 10.1.1.2 CONSENT PROCEDURES AND DOCUMENTATION

Informed consent is a process that is initiated prior to the individual's agreeing to participate in the study and continues throughout the individual's study participation. Consent forms will be Institutional Review Board (IRB)-approved and the participant will be asked to read and review the document. The investigator will explain the research study to the participant and answer any questions that may arise. A verbal explanation will be provided in terms suited to the participant's comprehension of the purposes, procedures, and potential risks of the study and of their rights as research participants. Participants will have the opportunity to carefully review the written consent form and ask questions prior to signing. The participants should have the opportunity to discuss the study with their family or surrogates or think about it prior to agreeing to participate. The participant will sign the informed consent document prior to any procedures being done specifically for the study. Participants must be informed that participation is voluntary and that they may withdraw from the study at any time, without prejudice. A copy of the informed consent document will be given to the participants for their records.

The informed consent process will be conducted and documented in the source document (including the date), and the form signed, before the participant undergoes any study-specific procedures. The rights and welfare of the participants will be protected by emphasizing to them that the quality of their medical care will not be adversely affected if they decline to participate in this study.

#### 10.1.2 STUDY DISCONTINUATION AND CLOSURE

This study may be temporarily suspended or prematurely terminated if there is sufficient reasonable cause. Written notification, documenting the reason for study suspension or termination, will be provided by the suspending or terminating party to <study participants, investigator, funding agency, the Investigational New Drug (IND) or Investigational Device Exemption (IDE) sponsor and regulatory authorities>. If the study is prematurely terminated or suspended, the Principal Investigator (PI) will promptly inform study participants, the Institutional Review Board (IRB), and sponsor and will provide the reason(s) for the termination or suspension. Study participants will be contacted, as applicable, and be informed of changes to study visit schedule.

Circumstances that may warrant termination or suspension include, but are not limited to:

- Determination of unexpected, significant, or unacceptable risk to participants
- Demonstration of efficacy that would warrant stopping
- Insufficient compliance to protocol requirements
- Data that are not sufficiently complete and/or evaluable
- Determination that the primary endpoint has been met
- Determination of futility

Study may resume once concerns about safety, protocol compliance, and data quality are addressed, and satisfy the sponsor, IRB and/or Food and Drug Administration (FDA).

